**Exploratory Data Analysis:**

- Plot outcomes across time across all index times
- 12-month enrollment for patient member months
- Histogram of age
- Univariate statistics, bivariate
- Conduct a Table 1
- Loss to follow-up

**Statistical Analyses:**

We will use a DID approach to study the impact of the E4 transition and generalized linear models to model the impact of the E4 transition via changes in outcomes. Time will be anchored at the month prior to the transition (e.g., index time is set to the month prior to the transition) for the E4 group. Each of the E4 transition members will be matched to two controls via propensity score methods. Non-E4 transition members will be assigned to an index date corresponding to their E4 transition match. We will not adjust for the matching in our models.

To match controls to E4 members, we will model the propensity score based on covariates we believe may be related to exposure: Gender, ACS Population Size, ACS Household Income in past 12 months, ACS Percent 25 years and older with a Bachelor's degree, ACS Percent White, and Year of birth. Then, we will obtain the log odds (logit) of the fitted values (e.g., estimates) of the propensity score for everyone (both E4 and possible controls) and order the log odds of the treatment (E4) group from largest to smallest (in decreasing order). For each E4 member, we will find the two nearest neighbor controls, e.g., the controls with the closest propensity score to that of the E4 individual with 12 months of continuous prior enrollment at the E4 individual's index date. After completing matching, we will check for covariate balance across groups based on the standardized mean differences and Kolmogorov–Smirnov statistic.

To address the zero-inflated and right skewed nature of the outcomes, we will use a two part-model. In the first stage of the two-part model, we will estimate the probability of the response being greater than zero and in the second stage we will model the non-zero portion. We will choose the most appropriate mean-variance relationship by performing goodness-of-fit tests (Pearson's correlation, Pregibon link, modified Park, and modified Hosmer-Lemeshow tests) on the outcomes. We will assume independence in the mean modeling to estimate the area under the curve change at 1 (primary), 2 and 3 years after index, and use the cluster bootstrap to obtain standard errors that account for repeated measurements within an individual (clustering on the individual level). We will adjust for individual-level (age, gender, and Elixhauser comorbidity score) and census ZIP-code level characteristics (educational attainment, median household income, race/ethnicity and urban residence) in all models.

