**Censoring Events:**

*Month at which an individual:*

- disenrolled for more than 1 month during study period
- turned 65 years of age

*Administrative censoring at:*

- end of study period (December 31st, 2019)

*Administrative left truncation at:*

- 24 months prior to index date

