**Inclusion criteria:**

*Individuals:*

- aged 0-64
- Continuously enrolled in an employer-sponsored health plan for at least 12 months (with one-month allowable gap) prior to the index date
  - For individuals in the exposed group, the index date is defined as the start date of value-based formulary implementation at the employer group level
  - For individuals in the control group, the index date is defined as the index date of the matched exposed individual

*Employer groups:*

- that transition to the value-based formulary if they transitioned **all** enrollees in that employer group (no individual selection)

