**Outcomes:**

*Primary outcome(s):* change in area under the curve one year after index date for all outcomes

*Secondary outcome(s):* change in area under the curve 2 and 3 years after index date for all outcomes

*Actual outcome list:*

Days supply of medications.

**Exposure:** VBF-E4 and non-VBF-E4

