**Covariates:**

*Adjustment variables:*

| Covariates   | Time of Measurement                     | Notes  | Specification  |
|--|---|--|--|
| Gender   | Month before E4 transition = index time |  | Indicator  |
| Age  | Index time                              | Centered   | Continuous   |
| Relationship to contract holder                        | Index time                              |  | Categorical 

• Contract Holder,

• Dependent,

• Spouse/Domestic Partner)

 |
| ACS  | Index time (or closest to this)         | For individuals with missing ACS variables at index time, set to closest observed value. | Quintile   |
| Percent 25 years old or older with a bachelor's degree |   |  | Quintile   |
| Median household income                                |   |  | Quintile   |
| Population size  |   |  | Quintile   |
| Percent White  |   |  | Quintile   |
| Funding Type   | Index time                              |  | Categorical (self, full)   |
| Elixhauser   | 12 months prior to transition time      |  | Categorical variable 

• 0

• 1

• >=2

                                  |
| Time from index date                                   | At all observations                     | 0 = index time, 1 = E4 transition month  | Continuous (-23 to 36)   |
| Post   | At all observations                     | Indicator for post period  | Indicator  |

|             |                     |   |   |
|-------------|---------------------|---|---|
| Seasonality | At all observations | Adjust for calendar year and separately adjust for calendar month | Categorical (1 through 12 for elig_mth) and (2015 through 2019 for elig_yr) |
|-------------|---------------------|---|---|

**Effect Modifiers:** None.

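### Only 12 pre-index months are guaranteed, but a 24-month group-specific pre-slope is fitted; if enrolment tenure differs between groups and relates to outcome, the AUC change can be biased

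*SAP*

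**What the plan says.** The relevant text is the same in Aims 1, 2 and 3.

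- **Eligibility** (Inclusion criteria): "Continuously enrolled in an employer-sponsored health plan for at least 12 months (with one-month allowable gap) prior to the index date".
- **Matching** (Statistical Analyses): the search is for "the controls with the closest propensity score to that of the E4 individual with 12 months of continuous prior enrollment at the E4 individual's index". The propensity score uses gender, four ACS variables and year of birth. Neither enrolment length nor any pre-index outcome is in it.
- **Window**: left truncation is at "24 months prior to index date" (Censoring Events), and time from index is "Continuous (-23 to 36") in the Covariates table.
- **Model**: both parts contain E4, post, month and all their interactions, so each group has its own pre-slope. There is no member effect or tenure covariate. Statistical Analyses states: "We will assume independence in the mean modeling to estimate the area under the curve change".
- **Primary outcome** (Outcomes): "change in area under the curve one year after index date for all outcomes". The contrast is not written as a formula.

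The balance check covers covariates, and tenure is not one. No balanced-panel rule or restricted-window sensitivity analysis is stated.

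**The concern.** The pre-period has two halves with different membership. Every eligible member contributes the later 12 months, apart from the allowed one-month gap. The earlier 12 months come only from members who joined sooner. Under working independence without member effects, the fitted pre-slope mixes change within members with change in who is present.

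A shift in membership that is the same in both groups cancels in the E4-control comparison. Nothing in the design makes it the same. Matched controls share the index date, which removes calendar differences, but turnover at employers that moved to E4 may differ from turnover in the control pool. Any part that does not cancel loads on E4*month.

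If the effect is the departure from the projected pre-trend (E4*post plus E4*post*month), that false slope is carried 12, 24 and 36 months forward. All outcomes in the three aims share the design, including the primary 1-year AUC. The planned bootstrap of members would not reveal the problem, because each resample reproduces the same tenure mix.

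**Working it through.** The SAP states no sample size, power or tenure figure, so there is no plan figure to reproduce. The windows and model terms below come from the SAP. Tenure shares and outcome ratios are assumptions, shown as a range.

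**1. Window.** Months -23 to 0 are 24 months. Eligibility secures 12 (taken as -11 to 0), which leaves 24 - 12 = 12 not guaranteed.

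**2. Mechanism.** Let S be a group's share with under 24 pre-index months, f(t) the fraction of these already enrolled at month t, and L and K the long- and short-tenure mean outcomes. With no true trend or effect, the observed mean is

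m(t) = [(1 - S)L + S f(t) K] / [(1 - S) + S f(t)].

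If K = L this is flat. If S and f(t) are equal in both groups, the two curves coincide. Both a tenure difference and a tenure-outcome association are needed.

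**3. Upper-end pattern, linear scale.** Suppose all short-tenure members enter at month -11, giving a between-group step of size s. A straight line on t = -23 to 0 has slope 72s/1150 = 0.0626s and intercept 1.22s at t = 0.

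| Horizon | Projected sum | True sum | Error |
|---|---|---|---|
| 12 months | 12(1.22s) + 78(0.0626s) = 19.5s | 12s | 7.5s |
| 24 months | 24(1.22s) + 300(0.0626s) = 48.1s | 24s | 24.1s |
| 36 months | 36(1.22s) + 666(0.0626s) = 85.6s | 36s | 49.6s |

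**4. Days' supply example (assumed).** Short-tenure share is 40% in E4 and 20% in controls; long-tenure members use 2 more days per month. Then s = -(0.40 - 0.20) x 2 = -0.4. Weighting each month by members present:

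| Entry of short-tenure members | 1 year | 2 years | 3 years |
|---|---|---|---|
| Spread evenly over months -22 to -11 | 1.8 days | 5.4 days | 10.9 days |
| All at month -11 | 3.1 days | 9.7 days | 19.8 days |

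Here the E4 counterfactual is projected too low, so a spurious increase appears.

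**5. The SAP's log-link Poisson mean.** Noise-free fit of the eight terms (intercept, E4, post, month and their interactions), true effect zero, positive part only. AUC change is the predicted E4 post-period AUC with against without E4*post and E4*post*month. Entry is gradual unless stated.

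| Long-tenure share, E4 / control | Short:long outcome | 1 year | 2 years | 3 years |
|---|---|---|---|---|
| 75% / 65% | 0.8 | -0.9% | -1.3% | -1.7% |
| 80% / 60% | 0.8 | -1.7% | -2.5% | -3.3% |
| 60% / 80% | 0.8 | +1.7% | +2.6% | +3.4% |
| 80% / 60% | 1.2 | +1.4% | +2.1% | +2.8% |
| 80% / 60% | 0.6 | -3.8% | -5.6% | -7.4% |
| 90% / 50% | 0.8 | -3.3% | -4.8% | -6.4% |
| 80% / 60%, all entering at -11 | 0.8 | -2.7% | -4.3% | -5.8% |
| 80% / 60% | 1.0 | 0 | 0 | 0 |
| 70% / 70% | 0.8 | 0 | 0 | 0 |

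**6. Other contrasts (80% / 60%, 0.8, gradual entry).** Fitted post 12 months minus fitted last 12 pre-months, E4 minus control, is off by about 0.13 on an AUC of about 1,150, or 0.01%. Measured instead against the mean of the whole 24-month pre-period, the 1-year contrast is off by about 0.8%.

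**7. Refit on months -11 to 0.** The spurious slope and AUC changes are 0 in every scenario. The pre-trend part of the 1-year standard error rises by sqrt[1/12 + 12²/143] / sqrt[1/24 + 18²/1150] = 1.044/0.569 = 1.8.

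**The case against.** The strongest reply is that the harm is conditional at every step. A reader might infer that unequal tenure by itself produces a false pre-trend. It does not: the bias is zero when tenure is unrelated to outcome, and age, gender, Elixhauser, relationship, funding type and the ACS variables may absorb part of any relation. The SAP gives no data on either condition. This stands.

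The second reply is that the SAP never defines the AUC contrast. This also stands: comparing fitted post 12 months with fitted last 12 pre-months would be almost unaffected under gradual entry. That is not a full escape. A contrast with the full pre-period is still affected, a 36-month post AUC has no pre-window of equal length in 24 months, and projecting the pre-slopes is what the E4*post*month structure most naturally suggests.

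Third, the larger errors of 3 and 20 days in the days' supply example require every short-tenure member to have exactly 12 months. Tenure between 12 and 23 months means spread-out entry, which gives 1.8 and 11 days. The larger figures are only an upper end for that example.

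Fourth, using all available pre-period data up to a cap is a common choice, and the planned outcome plots might show a break. Those plots are exploratory, and no listed item compares tenure between groups or triggers any action.

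**Conclusion.** The structural mismatch holds in all three aims: 12 months guaranteed, a 24-month group-specific pre-slope fitted, and tenure neither matched, adjusted for nor balance-checked. The consequence is a possible bias, not a demonstrated one. It needs three things together:

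- different tenure mixes in E4 members and controls;
- a tenure-outcome relation that survives covariate adjustment;
- a contrast that depends on the fitted pre-slopes.

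Under moderate assumed values (long-tenure shares of 75-80% against 60-65%, short-tenure outcome 0.8 times long-tenure, gradual entry), the spurious AUC change is about 1-2% at 1 year and 2-3% at 3 years. Its sign depends on which group has longer tenure and how tenure relates to outcome. Stronger assumptions gave up to about 4% at 1 year with gradual entry. These figures come from the Poisson positive-part mean alone; the full two-part model and the Gamma model of Aim 2 were not evaluated.

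The documents do not support saying that the planned estimate is biased, or in which direction. They also do not support attributing the problem to the January 2015 data start: controls take their match's index date, so that limit adds no between-group difference. The case for acting is that the check and repair are cheap and protect the primary outcome in every aim.

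**What to change.** In the Statistical Analyses section of each aim:

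1. Count each person's observed enrolled months in the -23 to 0 window. Choose the two nearest neighbours on the logit within bands of this count (for example 12, 13-17, 18-23 and 24), or add the count to the propensity score.
2. Include the count in the standardized-mean-difference and Kolmogorov–Smirnov balance check.
3. Prespecify a sensitivity refit with the pre-period limited to months -11 to 0, which every eligible member contributes apart from the allowed one-month gap.
4. Write out the AUC-change contrast, so that its dependence on the pre-slopes is explicit.

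The cost is SAP wording and one variable derivable from the enrolment records already needed for eligibility. Propensity-score distances will be slightly larger in sparse bands. The refit has a less precise pre-slope (about 1.8 times the pre-trend part of the standard error at 1 year), which is why it is offered as a sensitivity analysis rather than a replacement. If tenure proves balanced, little is lost.

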**Statistical Analyses:**

We will use a DID approach to study the impact of the E4 transition and generalized linear models to model the impact of the E4 transition via changes in outcomes. Time will be anchored at the month prior to the transition (e.g., index time is set to the month prior to the transition) for the E4 group. Each of the E4 transition members will be matched to two controls via propensity score methods. Non-E4 transition members will be assigned to an index date corresponding to their E4 transition match. We will not adjust for the matching in our models.

To match controls to E4 members, we will model the propensity score based on covariates we believe may be related to exposure: Gender, ACS Population Size, ACS Household Income in past 12 months, ACS Percent 25 years and older with a Bachelor's degree, ACS Percent White, and Year of birth. Then, we will obtain the log odds (logit) of the fitted values (e.g., estimates) of the propensity score for everyone (both E4 and possible controls) and order the log odds of the treatment (E4) group from largest to smallest (in decreasing order). For each E4 member, we will find the two nearest neighbor controls, e.g., the controls with the closest propensity score to that of the E4 individual with 12 months of continuous prior enrollment at the E4 individual's index date. After completing matching, we will check for covariate balance across groups based on the standardized mean differences and Kolmogorov–Smirnov statistic.

To address the zero-inflated and right skewed nature of the cost outcomes, we will use a two part-model. In the first stage of the two-part model, we will estimate the probability of the response being greater than zero and in the second stage we will model the non-zero portion. We will choose the most appropriate mean-variance relationship by performing goodness-of-fit tests (Pearson's correlation, Pregibon link, modified Park, and modified Hosmer-Lemeshow tests) on the primary cost outcome. We will assume independence in the mean modeling to estimate the area under the curve change at 1 (primary), 2 and 3 years after index, and use the cluster bootstrap to obtain standard errors that account for repeated measurements within an individual (clustering on the individual level). We will adjust for

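### The formulary switch happens to whole employer groups, but the bootstrap resamples individual members, so the standard errors in all three aims are likely too small

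*SAP*

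**What the plan says.** The Inclusion criteria, identical in Aims 1, 2 and 3, set exposure by employer. For exposed members, "the index date is defined as the start date of value-based formulary implementation at the employer group level". A switching employer counts only if it moved all "enrollees in that employer group (no individual selection"). For controls, "the index date is defined as the index date of the matched exposed individual", so their dates also trace back to an employer's date.

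The Statistical Analyses section of each aim then states: "We will assume independence in the mean modeling", and says the plan will "use the cluster bootstrap to obtain standard errors that account for repeated measurements within an individual (clustering on the individual level"). The stated purpose is correlation within one person over time.

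The Model sections contain E4, post, month and their interactions, age, gender, Elixhauser score, relationship, funding type and four ZIP-level variables. No term or variance component identifies the employer. The Covariates tables list "Relationship to contract holder" with contract holder, dependent and spouse or partner as levels, so relatives on one contract enter as separate individuals. On matching the SAP says: "We will not adjust for the matching in our models".

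**The concern.** The variance should be estimated at the level at which exposure was assigned, or above it. Here everyone in a switching employer moves together on one date. Anything else that changes for that workforce around the same time, such as another benefit change or staff turnover (examples, not facts from the SAP), moves all those members together. It falls on the E4-by-post and E4-by-post-by-month terms that define the effect. A bootstrap over individuals treats each member's share of that movement as independent information.

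The same sentence governs the standard error of every primary and secondary area-under-the-curve outcome in all three aims. The error is anti-conservative, and no planned sensitivity analysis would expose it.

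**Working it through.** **Inputs.** From the SAP: two controls per E4 member (Statistical Analyses), employer-level exposure and index date (Inclusion criteria), and individuals as the resampling unit (Statistical Analyses). The SAP states no sample size, significance level, employer count, employer size or intraclass correlation (ICC), so it has no figure to reproduce. Assumed: a two-sided 5% level, *m* = 10 to 500 members per employer, and an ICC *ρ* of 0 to 0.03. Here *ρ* is the within-employer correlation of a member's pre-to-post *change*; a constant employer level largely cancels in the before-after contrast.

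**Formulas.** The design effect is D = 1 + (m − 1)ρ. With *n* exposed members and 2*n* controls, the true variance is proportional to D_E + 0.5·D_C, while the individual bootstrap targets 1 + 0.5 = 1.5. So:

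- variance ratio R = (D_E + 0.5·D_C)/1.5
- planned SE / correct SE = 1/√R
- actual error = 2·[1 − Φ(1.96/√R)]

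The lower bound takes unclustered controls (D_C = 1). The upper bound takes controls clustered like the E4 group (D_C = D_E, so R = D_E).

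**One case worked.** For m = 100 and ρ = 0.01, D_E = 1 + 99 × 0.01 = 1.99.

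- Lower: R = (1.99 + 0.5)/1.5 = 1.66; SE ratio 0.78; 1.96/√1.66 = 1.52; error 12.8%.
- Upper: R = 1.99; SE ratio 0.71; 1.96/√1.99 = 1.39; error 16.5%.

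| m | ρ | R (lower–upper) | planned SE / correct SE | actual error |
|---|---|---|---|---|
| any | 0 | 1 | 1 | 5.0% |
| 10 | 0.01 | 1.06–1.09 | 0.97–0.96 | 5.7–6.1% |
| 100 | 0.002 | 1.13–1.20 | 0.94–0.91 | 6.5–7.3% |
| 100 | 0.01 | 1.66–1.99 | 0.78–0.71 | 12.8–16.5% |
| 100 | 0.03 | 2.98–3.97 | 0.58–0.50 | 25.6–32.5% |
| 500 | 0.01 | 4.33–5.99 | 0.48–0.41 | 34.6–42.3% |

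Correlation within a contract alone (3 members, ICC 0.05) gives R = 1.07 to 1.10 and an error of 5.8 to 6.2%, which is minor.

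**Simulation, linear difference-in-differences.** 30 exposed and 60 control employers of 100 members each, no true effect, 3,000 runs:

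| ρ | SE from members | SE from employer means | error, members | error, employers |
|---|---|---|---|---|
| 0 | 0.0224 | 0.0223 | 5.2% | 5.5% |
| 0.005 | 0.0224 | 0.0272 | 11.3% | 5.8% |
| 0.01 | 0.0223 | 0.0313 | 16.1% | 5.1% |
| 0.02 | 0.0223 | 0.0384 | 25.8% | 5.8% |

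**Simulation, two-part model.** Logit plus Gamma with log link and a 12-month area-under-the-curve contrast, reduced to group-by-period terms. 40 E4 employers of 100 and 200 control employers of 40, linearised bootstrap SE, about 16,000 null runs per setting. Error with individual versus employer clustering:

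- 5.1% vs 5.5% with only a time-constant employer effect (ICC of change 0)
- 7.8% vs 5.7% at ICC 0.003
- 15.4% vs 5.6% at ICC 0.012
- 34.8% vs 5.4% at ICC 0.044

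**Few switching employers.** Change-score simulation, 100 members per E4 employer, ICC 0.03, 20,000 runs. With 5, 10, 20 and 40 E4 employers, an employer-level SE with a normal reference gives errors of 11.7, 8.2, 6.7 and 5.8%. A *t* reference with (E4 employers − 1) degrees of freedom gives 2.7, 4.0, 4.6 and 4.9%.

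**The case against.** The strongest reply is that the size is unknown. The illustration runs from negligible to severe, and nothing in the SAP places this study within it. Difference-in-differences largely removes constant employer effects, so all the inflation depends on employer-specific change that nobody has measured. Controls are matched individually and not by employer, so they may be spread thinly, which would favour the lower figures. The SAP plans standard errors and states no significance level, so the error rates rest on an assumed 5%. The two-part simulation omits the month slopes, covariates and censoring, and its Gamma second part corresponds to Aim 2 only; Aims 1 and 3 specify Poisson.

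All of this stands as a limit on the *size*. None of it changes the direction: for any positive correlation of change within employers, the planned standard error is too small.

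Two further replies are weaker.

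- Funding type and the ZIP-level variables might absorb employer effects. But funding type has two levels, and all of these enter as index-time main effects without a post interaction, so they cannot capture employer-specific change. Calendar terms are common to all employers.
- Leaving the matching out of the models may push standard errors slightly upward. That offset is unquantified and does not replace variance at the level of assignment.

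The missing employer term is not a defect in itself. A working-independence mean model is acceptable if the resampling unit is right.

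**Conclusion.** The concern holds. The SAP assigns exposure by employer and explicitly fixes the variance at "clustering on the individual level", and no other section corrects for this. The rule is wrong as written; it is not a detail left to another document. It must be fixed, because it governs every reported interval in all three aims.

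Confidence is high in the mismatch of levels and in the direction of the error. The amount cannot be derived from the SAP and may differ by outcome. It grows with employer size and with the correlation of change, and vanishes if that correlation is zero. Changing the clustering level costs little when the correlation is nil and switching employers are numerous (5.5% against 5.1% error in the two-part simulation with 40 E4 employers).

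**What to change.** In the Statistical Analyses section of each aim, replace individual-level clustering with a cluster bootstrap over employer groups:

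- Fix each member's employer at the index date. When an employer is drawn, take all its analysed members and all their months. Draw E4 and control employers separately. This also covers correlation within a contract and, provided each person belongs to one employer, within a person.
- State whether a control may be reused. If so, say how one with more than one index date, and possibly more than one employer, is assigned to a cluster.
- State whether the matched sample is held fixed or matching is repeated in each resample. Repeating it would be substantially more work.
- Fix the small-cluster method before outcomes are analysed. A *t* reference with (E4 employers − 1) degrees of freedom, used whatever the count, avoids having to define few, though it is conservative with very few employers (2.7% at 5). A score-based wild cluster bootstrap or an employer-level permutation are alternatives; name one.
- Report the number of E4 and control employer groups, so that readers can judge the reference distribution.

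The cost is a wording change in three places, an employer identifier at index in the analysis file, and a stated rule for matched sets. Point estimates do not change. Intervals will usually be wider, and analysis effort rises slightly if the matched sample is held fixed.
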